6.2.1.3 Follow-up Visits

Patients will have monthly visits for 3 months following the last dose of ipilimumab. The following assessments will be performed at this visit:

- Physical Exam, including weight
- Toxicity and concomitant medications assessment
- Performance Status assessment
- Laboratory tests: CBC with differential and platelets, serum chemistry (SGOT, SGPT, alk phos, total bili, LDH, electrolytes, glucose, BUN, Cr, amylase, lipase), PSA, TSH, T4
- Immune monitoring – all patients at UCSF and MD Anderson
- Additional immune monitoring – MD Anderson patients ONLY
- Immune worksheet

6.2.2 Study Completion or Early Discontinuation Visit

Patients will continue on therapy, including any re-induction therapy, until any one of the following events occurs:

- Progressive disease, as defined in section 7.1
- Patient withdraws consent
- Treating physicians' discretion

For all patients without significant AEs, PSA and/or objective progression will not require the patient to come off study until at least three cycles of therapy have been administered.

Patients may choose to withdraw at any time. No further protocol therapy will subsequently be given. At the time of study early withdrawal, the reason for early withdrawal and any new or continuing adverse events should be documented.

6.2.3 Study Drug Discontinuation

If study drug administration is discontinued, the reason for discontinuation will be recorded. Patients will return for a 30 day follow up visit (\pm 5 days) as described in section 6.2.1.c.

Subjects MUST be discontinued from study therapy AND withdrawn from the study for the following reasons:

- Withdrawal of informed consent (subject's decision to withdraw for any reason)
- Any clinical adverse event, laboratory abnormality or intercurrent illness which, in the opinion of the investigator, indicates that continued treatment with study therapy is not in the best interest of the subject
- Pregnancy: Partners of WOCBP should be instructed to contact the investigator immediately if they suspect their partner might be pregnant (e.g., missed or late menstrual period) at any time during study participation. The investigator must immediately notify BMS in the event of a confirmed pregnancy in a partner participating in the study.
- Termination of the study by Bristol-Myers Squibb (BMS) and/or Dendreon.
- Imprisonment or the compulsory detention for treatment of either a psychiatric or physical (e.g., infectious disease) illness.

7 EFFICACY AND SAFETY ASSESSMENTS

7.1 Efficacy Assessment

7.1.1 Immune Response Endpoints

The primary immune study hypothesis is to assess the frequency of observing an IgG antibody response to PAP and/or PA2024 at baseline and at week 20 for each of the two ipilimumab schedules. The IgM and IgG antibody responses to PAP and PA2024 will both be assessed with an ELISA assay at baseline and week 20 after the start of protocol therapy. T cell responses to PAP and PA2024 will be assessed with an ELISPOT assay at baseline and at week 20 after the start of protocol therapy.

7.1.2 Clinical Response Endpoints

Ipilimumab is expected to trigger immune-mediated responses, which require activation of the immune system prior to the observation of clinical responses. Such immune activation may take weeks to months to be evident. Some patients have had objective volume increase of tumor lesions or other disease parameters within 12 weeks following the start of ipilimumab, which is

subsequently followed by objective clinical responses^{9,45}. Early in the treatment, patients may not have had sufficient time to develop the required immune activation or, in some patients, tumor volume or other disease parameter increases may represent infiltration of lymphocytes into the original tumor or blood. In conventional studies, such tumor volume or relevant laboratory parameter increases during the first 12 weeks of the study would constitute PD and lead to discontinuation of treatment as well as subsequent imaging to detect response, thus disregarding the potential for subsequent immune-mediated clinical response.

Therefore, patients with tumor volume increase detected or lack of laboratory parameter response documentation prior to week 12 but without rapid clinical deterioration should continue on treatment with ipilimumab and continue to be imaged to allow detection of a subsequent tumor response. This will improve the overall assessment of the clinical activity of ipilimumab and will more likely capture its true potential to induce clinical responses. Clinical assessment will be made using PSA response and radiographic response using standard irRC.⁹

7.1.3 Clinical Efficacy Evaluation

Patients will have PSA measurements on day 1 of every cycle prior to treatment. PSA decline will be evaluated according to the recommendations from PSA Working Group (PSAWG)³⁹. Although response in this study is defined as a PSA decline, progressive disease is defined as progression by either PSA or objective progression. Bone scans and CT scans will be repeated every 12 weeks and at the time of PSA progression. Each category (measurable, non-measurable, and PSA) will be assessed and reported independently. Measurable disease/target lesions and non-measurable disease/non-target lesions will be evaluated according to the irRC.⁹

7.1.3.1 Definition of PSA Decline

All patients, with or without measurable disease, will be evaluated for PSA decline.

Patients with disease that is not measurable will be eligible for this study and will be assessed for response based on changes in PSA and serial bone scans. The baseline serum PSA must be at least 2 ng/mL.

30% PSA Decline: PSA decline of at least 30% from baseline confirmed by a second measurement at least 4 weeks later. The reference for these declines should be a PSA measured within 2 weeks prior to starting therapy.

50% PSA Decline: PSA decline of at least 50% from baseline confirmed by a second measurement at least 4 weeks later. The reference for these declines should be a PSA measured within 2 weeks prior to starting therapy.

PSA Progression: If at least a 50% PSA decline has been achieved, PSA progression occurs when the PSA has increased to 25% above the nadir and the increase in the absolute-value PSA level is at least 2 ng/mL, or back to baseline, whichever is lower, on at least 2 consecutive measurements at least 1 week apart. For patients without a PSA decline of this magnitude, or without any decline in PSA, progression will be defined by a 25% increase over baseline or nadir PSA (whichever is lower) and an increase in the absolute value PSA level by at least 2 ng/mL, on at least 2 consecutive measurements, after 12 weeks of therapy. For all patients without SigAEs, PSA and/or objective progression will not require the patient to discontinue study treatment until at least three cycles of therapy have been administered.

PSA Decline Duration: The PSA decline duration commences on the date of the first 50% decline in PSA. The response duration ends when the PSA value increases by 50% above the nadir, provided that the increase in the absolute-value PSA level is at least 2 ng/mL or back to baseline, whichever is lower. If a patient does not progress for the duration of the study, his data will be censored at the time of last PSA follow-up.

Progressive Disease: Defined by PSA progression or by objective progression (based on RECIST 1.1 criteria or the appearance of two or more new lesions on bone scan, confirmed 6 or more weeks later) more than three months after the initiation of therapy. Although response in this study is defined as a PSA decline, progressive disease is defined as progression by either PSA or objective progression.

Time to PSA Progression: The start of the time to PSA progression is the day treatment is initiated. The end date is the time of PSA progression as defined above. If a patient does not progress for the duration of the study, his data will be censored at the time of last PSA follow-up.

7.1.3.2 *Definition of Measurable and Non-Measurable Lesions*

Measurable Disease/Target Lesions

All measurable lesions (lesions that can be accurately measured in at least one dimension, longest diameter to be recorded, as ≥ 10 mm with spiral CT) up to a maximum of 5 lesions per organ and 10 lesions total, representative of all involved organs, should be identified as target lesions and recorded and measured at baseline. Target lesions should be selected on the basis of their size (lesions with the longest diameter) and the suitability for accurate repeated measurements (either by imaging techniques or clinically). The sum of the products of the two largest perpendicular diameters (SPD) of all index lesions (5 lesions per organ, up to 10 visceral lesions) is calculated. At each subsequent tumor assessment, the SPD of the index lesions and of new, measurable lesions ($\geq 5 \times 5$ mm; up to 5 new lesions per organ and 10 visceral lesions) are added together to provide the total tumor burden:

$$\text{Tumor Burden} = \text{SPD}_{\text{index lesions}} + \text{SPD}_{\text{new, measurable lesions}}.$$

The overall response according to the irRC is derived from time-point response assessments (based on tumor burden) as follows:

- Complete Response (CR): complete disappearance of all lesions (whether measurable or not, and no new lesions)
 - confirmation by a repeat, consecutive assessment no less than 4 wks from the date first documented
- Partial Response (PR), decrease in tumor burden $\geq 50\%$ relative to baseline
 - confirmed by a consecutive assessment at least 4 wks after first documentation
- Stable Disease (SD), not meeting criteria for CR or PR, in absence of PD
- Progressive Disease (PD), increase in tumor burden $\geq 25\%$ relative to nadir (minimum recorded tumor burden)
 - confirmation by a repeat, consecutive assessment no less than 4 wks from the date first documented

Patients were considered to have PR or SD even if new lesions were present, as long as they met the respective thresholds of response as described above. Furthermore, patients were not considered to have PD if new lesions were present and the tumor burden of all lesions did not increase by $\geq 25\%$. In contrast to CR, PR, and PD, a response of SD does not require confirmation. It is important to note that CR, PR, and SD include all patients with CR, PR, or SD by WHO criteria as well as those patients that shift to these irRC categories from WHO PD. Patients with SD, particularly those with slow-declining tumor burden $\geq 25\%$ from baseline at the last tumor assessment, are considered clinically meaningful because they show an objectively measurable reduction in tumor burden without reaching the 50% threshold that defines PR (it represented an objectively measured reduction not commonly observed in the natural history of advanced melanoma patients).

Confirmation: To be assigned a status of PR or CR, changes in tumor measurements must be confirmed by repeat studies no less than 4 weeks after the criteria for response are first met

Duration of overall response: The duration of overall response is measured from the time measurement criteria are met for CR/PR (whichever is first recorded) until the first date that recurrent or progressive disease is objectively documented (taking as reference for progressive disease the smallest measurements recorded since the treatment started).

Non-measurable Disease/Non-Target Lesions

All non-measurable lesions (including small lesions, longest diameter < 20 mm with conventional techniques or < 10 mm with spiral CT scan and truly non-measurable lesions such as bone lesions) should be identified as non-target lesions and should also be recorded at baseline. Measurements of these lesions are not required, but the presence or absence of each should be noted throughout follow-up.

Complete Response (CR): The disappearance of all non-target lesions

Incomplete Response/Stable Disease (IR/SD): The persistence of one or more non-target lesion(s) without unequivocal progression of existing non-target lesions

Progressive Disease (PD): The appearance of one or more new lesions and/or unequivocal progression of existing non-target lesions. For bone scans, the appearance of 2 or more new lesions is required. These lesions should be re-evaluated 6 or more weeks later to confirm progressive disease. Increased intensity of uptake in previously abnormal areas on bone scans is not considered progressive disease, unless the lesions seen on the correlative imaging studies performed of this area meet the criteria for progression.

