3.3 Reinduction Treatment

Patients who experience a clinical response to treatment during the first 12 weeks of ipilimumab treatment, but then develop subsequent progression of their disease after the initial 12 weeks of ipilimumab and who have not experienced unacceptable toxicity (refractory Grade > 3 irAEs) can be offered reinduction therapy with ipilimumab with up to 4 doses Q3 wks at the same dose level.

Following discontinuation of study therapy, subjects will complete a 30-day off study visit and then enter into follow up. Subjects who discontinue ipilimumab treatments should be followed until death or closure of the study (whichever is first). Subjects who are no longer receiving ipilimumab because of clinical progression and who have switched to alternative treatment are not followed formally except to record the date of death.

[figure not shown]

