5.4.6 Discontinuation of Ipilimumab Treatment

The following treatment-related non-neurological adverse events require permanent discontinuation of ipilimumab:

- Any \geq Grade 2 eye pain or reduction of visual acuity that does not respond to topical therapy and does not improve to \leq Grade 1 severity within 2 weeks of starting therapy, OR requires systemic treatment.
- Any \geq Grade 3 bronchospasm or other hypersensitivity reaction.

- Any other \geq Grade 3 non-skin related adverse event with the exception of events listed below under “Exceptions to Permanent Discontinuation”.
- Any \geq Grade 4 laboratory abnormalities, except AST, ALT, or Total Bilirubin
- AST or ALT $> 5 \times$ ULN
- Total Bilirubin $> 3 \times$ ULN
- Any other \geq Grade 4 adverse event
- *Withhold of ipilimumab for greater than 60 days due to treatment related toxicity*
- Any adverse event, laboratory abnormality or intercurrent illness, which, in the judgment of the investigator, presents a substantial clinical risk to the patient with continued dosing.
- The development of progression in the global tumor burden and/or clinical deterioration of subject’s condition such that further benefit from ipilimumab dosing is unlikely or requires a change of therapy.

The following neurological adverse event requires permanent discontinuation of ipilimumab and defines unacceptable neurotoxicity:

- Any motor neurologic toxicity \geq Grade 3 regardless of causality
- Any \geq Grade 3 treatment related sensory neurologic toxicity

Please refer to the Appendices for specific treatment algorithms.

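### Men who switch therapy for clinical progression, or before a first PSA or bone-scan progression is confirmed, are censored as if still doing well, so the median time to progression per arm may read too long

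*Combined protocol and SAP*

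**What the plan says.** **Events.** Section 7.1.3.1 ends time to PSA progression at PSA progression and nothing else: "The end date is the time of PSA progression as defined above". After a decline of at least 50%, the rise must be seen "on at least 2 consecutive measurements at least 1 week apart". Without such a decline it must be seen "on at least 2 consecutive measurements, after 12 weeks of therapy". The same section defines progressive disease as PSA progression or objective progression more than three months after therapy begins. Objective progression is by RECIST 1.1 or by "the appearance of two or more new lesions on bone scan, confirmed 6 or more weeks later". Under the irRC assessment in 7.1.3.2, progression needs "confirmation by a repeat, consecutive assessment no less than 4 wks from the date first documented". Neither clinical deterioration nor a change of therapy is an event in any of these definitions.

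**Censoring.** For time to PSA progression: "If a patient does not progress for the duration of the study, his data will be censored at the time of last PSA follow-up". The synopsis lists a median time to progression, counted after 4 cycles, without any censoring rule.

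**Stopping and follow-up.** Section 5.4.6 lists among the reasons to end ipilimumab: "The development of progression in the global tumor burden and/or clinical deterioration". Section 3.2 foresees clinical progression that warrants other treatment. Under 3.3, men no longer on ipilimumab because of clinical progression and "who have switched to alternative treatment are not followed formally except to record the date of death".

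**Analysis.** Section 9.3.2.1 applies Kaplan-Meier to time to PSA progression. It presents the median time to progression per arm, with a 95% interval, as the summary of clinical efficacy.

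**The concern.** Kaplan-Meier assumes that a man censored at a given time has the same later risk as the men still under observation. A man who changes therapy because he is getting worse does not. If the event needs a second assessment, and formal follow-up ends before that assessment is due, the plan files him with the men who are stable.

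The visit schedule makes this plausible. After three monthly visits, follow-up is every 12 weeks (Sections 3 and 6.1), so a first qualifying PSA may wait about 12 weeks for its scheduled confirmation. Section 7.1.3.1 also does not say whether confirmed progression is dated at the first or the second value.

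At stake is the main time-to-event description of clinical activity. The research hypothesis in 1.1 names time to progression, with PSA decline, as the measure of clinical efficacy. In an open-label trial, the two arms may also differ in how readily men are switched, and their medians would then be lengthened by different amounts.

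**Working it through.** **1. The plan's own figures.** No median, event count or power is stated for time to progression, so there is nothing to reproduce for this endpoint. The design figure that exists, 27 per arm with 81% power (9.1.2), belongs to the antibody response. With n = 27 and a null rate of 15%, the smallest count with an upper tail of at most 0.025 is 9: P(X ≥ 9) = 0.0138, while P(X ≥ 8) = 0.0398. At 40% the power is P(X ≥ 9) = 0.816. The figure reproduces, and nothing below changes it.

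**2. Who is affected, under the text as written.**

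- *Stops ipilimumab only:* stays in follow-up (3.3, 4.3, and the calendar note that runs quarterly visits to progression or 2 years) and has a 30-day visit (3.3, 6.2.3). The calendar lists PSA at the off-study visit. Stopping alone does not censor him.
- *Stops for clinical progression and switches:* followed only for death and, without two qualifying PSA values, censored at the last PSA.
- *First qualifying PSA, then switch or death before the second value:* censored at the last PSA.
- *New bone lesions, then switch or death before the re-scan:* not a PSA event, and not confirmed for the composite.
- *Soft-tissue progression by RECIST 1.1 after three months:* may count for the composite unconfirmed, because the 6-week condition reads most naturally as attached to the bone scan.

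**3. Size.** Let true progression times be exponential with hazard λ and median m = ln 2/λ. Let a share f of progressions be censored at the time they would have counted. Kaplan-Meier then estimates exp(−(1−f)λt), whose median is ln 2/((1−f)λ) = m/(1−f). Both f and m are assumptions. The last column comes from simulated arms of 27 men with true medians of 12, 18 and 26 weeks. Visits were every 3 weeks to week 12, every 4 weeks to week 24, then every 12 weeks to about 2 years. The 12-week start and the confirmation delay were left out.

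| Assumed f | Factor 1/(1−f) | Reported median if m = 26 weeks | Simulated arms in which the median rose |
|---|---|---|---|
| 5% | 1.05 | 26/0.95 = 27.4 | 20–22% |
| 10% | 1.11 | 26/0.90 = 28.9 | 36–41% |
| 20% | 1.25 | 26/0.80 = 32.5 | 61–66% |
| 30% | 1.43 | 26/0.70 = 37.1 | 78–84% |

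If all 27 men progress, f of 10% is 0.10 × 27 = 2.7 men and f of 20% is 5.4 men. In large simulated samples of 20,000 without the visit grid, the median moved from 26.1 to 29.1 weeks at 10%, 26.2 to 32.2 at 20%, and 25.9 to 36.7 at 30%, in line with the formula.

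**4. Direction and limits.** In the simulations the median never fell. That ordering holds when the last PSA falls on or after the date at which the event would have been counted. If the last PSA precedes the switch decision, the risk set shrinks early and the curve can be slightly lower between the two dates. When only men progressing after week 36 were affected, the large-sample median did not move at all.

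**5. Unequal arms.** With the same true median of 26 weeks, f of 10% in one arm and 20% in the other would give 28.9 and 32.5 weeks, an apparent gap of 3.6 weeks made by censoring alone.

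**The case against.** The strongest reply is that the plan keeps most men under observation. Those who discontinue ipilimumab are to be followed until death or study closure, tests are to continue where possible, and the 30-day PSA can supply the second value. After a 50% decline, the values need be only one week apart. Section 3.2 also asks for a 12-week tumor assessment even after early clinical progression. This stands, and it reduces f. It does not remove the gap. The 12-week scan does not change the event definition. As 3.3 words it, the 30-day visit follows the end of study therapy, so it does not help a man who switches later, during quarterly follow-up.

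A second reply is that 3.2 and 7.1.2 deliberately discount early worsening, because responses may follow it, and that clinical progression is a subjective event in an open-label trial. This also stands, and it is why the confirmed-only definition should be kept.

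A third is that the endpoint is secondary, descriptive and reported per arm in a non-comparative trial, with no planned test of the medians. That is correct and limits the consequence.

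A reader might go further and infer that every man who stops for clinical deterioration is censored, that all scan progressions need confirmation, or that censoring a death without progression is itself an error. The documents do not support the first two, for the reasons in step 2 of the working. The third is ordinary practice for time to progression. The problem there is only the man who had a first, unconfirmed progression before he died.

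**Conclusion.** The point holds for a defined group: men who switch therapy for clinical progression, and men who switch or die with a first PSA or bone-scan progression unconfirmed. For time to PSA progression, their informative censoring follows from the written rule. For the composite in the synopsis, the defect is a missing rule, and the same result is likely but inferred.

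It would be tempting to say that the median is overstated. The documents support only that it can be too long or unchanged. At an assumed f of 10% the simulated median stayed put in more than half of the arms. The factors of 1.11 and 1.25 rest on exponential times, affected men spread evenly over time, and assumed values of f. The true size cannot be computed from the plan and may be zero. The correction is worth making because this median is the stated summary of clinical efficacy, but it affects no primary conclusion.

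**What to change.** In 7.1.3.1 and 9.3.2.1, keep the confirmed-only definition and report beside it, for each arm, an analysis of time to progression that also counts as events:

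- (a) a switch of therapy for clinical progression, dated at the decision to switch;
- (b) a first PSA or bone-scan progression left unconfirmed because the man died or started other therapy, dated at first documentation.

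In addition:

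- date confirmed progression at its first documentation;
- apply the plan's existing three-month/12-week window in the same way to both analyses, and say how a switch inside that window is handled;
- write a censoring rule for the composite endpoint;
- report the number of men in (a) and (b) per arm, which replaces the assumed f with an observed one.

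The cost is analysis wording. The reason for discontinuation (6.2.3) and the date of death (3.3) are already recorded; the date of the switch decision should be confirmed as captured. No visit, treatment rule or sample size changes. The downside is a somewhat shorter median in the added analysis and a less objective event in an open-label trial. Showing both analyses lets the reader judge.
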